6. STUDY POPULATION

Prospective approval of protocol deviations to recruitment and enrolment criteria, also known as protocol waivers or exemptions, is not permitted.

6.1. Inclusion Criteria

Participants are eligible to be included in the study only if all of the following criteria apply:

Age

1. Participant must be over 65 years of age inclusive, at the time of signing the informed consent.

Type of Participant and Disease Characteristics

2. Participants who are overtly healthy as determined by medical evaluation including medical history, physical examination, laboratory tests, and ECG. A subject with a clinical abnormality or laboratory parameter(s) which is/are not specifically listed in the inclusion or exclusion criteria, outside the reference range for the population being studied may be included only if the investigator in consultation with the Medical Monitor if required agree that the finding is unlikely to introduce additional risk factors and will not interfere with the study procedures.

3. Participants whose peripheral blood neutrophil counts and hematocrit values are within normal range at screening visit.

Weight

4. Body weight \geq 50 kg and body mass index (BMI) within the range 18.5 – 24.9 kg/m² (inclusive).

Sex

5. Japanese Male

A male participant must agree to use contraception as detailed in Appendix 5 of this protocol during the treatment period and until follow up visit.

Informed Consent

6. Capable of giving signed informed consent as described in restrictions listed in the informed consent form (ICF).

6.2. Exclusion Criteria

Participants are excluded from the study if any of the following criteria apply:

Medical Conditions

1. History or presence of cardiovascular, respiratory, hepatic, renal, gastrointestinal, endocrine, hematological, or neurological disorders capable of significantly altering the absorption, metabolism, or elimination of drugs; constituting a risk when taking the study treatment; or interfering with the interpretation of data
2. Abnormal blood pressure as determined by the investigator
3. Alanine Aminotransferase (ALT) $> 1.5 \times$ upper limit of normal (ULN)
4. Bilirubin $> 1.5 \times$ ULN (isolated bilirubin $> 1.5 \times$ ULN is acceptable if bilirubin is fractionated and direct bilirubin $< 35\%$)
5. Current or chronic history of liver disease, or known hepatic or biliary abnormalities (with the exception of Gilbert's syndrome or asymptomatic gallstones)
6. QTcF > 450 msec

NOTES:

- The QTc is the QT interval corrected for heart rate according to Fridericia's formula (QTcF), and/or another method, machine-read or manually over-read.
- The specific formula that will be used to determine eligibility and discontinuation for an individual subject should be determined prior to initiation of the study. In other words, several different formulae cannot be used to calculate the QTc for an individual subject and then the lowest QTc value used to include or discontinue the subject from the trial.

- For purposes of data analysis, QTcF, another QT correction formula, or a composite of available values of QTc will be used as specified in the Reporting and Analysis Plan (RAP).

Prior/Concomitant Therapy

7. Past or intended use of over-the-counter or prescription medication including herbal medications and proton pump inhibitor (PPI) within 14 days prior to dosing. Specific medications listed in Section 7.7 may be allowed

Prior/Concurrent Clinical Study Experience

8. History of donation of blood or blood products \geq 400 mL within 3 months or \geq 200 mL within 1 month prior to screening
9. Exposure to more than 4 new chemical entities within 12 months prior to the first dosing day
10. Current enrollment or past participation within the last 30 days before signing of consent in this clinical study involving an investigational study treatment or any other type of medical research

Diagnostic assessments

11. The subject with positive Serological test for syphilis (Rapid Plasma Reagins [RPR] and Treponema pallidum hemagglutination test [TPHA]), Human immunodeficiency virus (HIV) Antigen/Antibody, Hepatitis B surface antigen (HBsAg), Hepatitis C virus (HCV) antibody, or Human T-cell lymphotropic virus type 1 (HTLV-1) antibody at screening
12. Positive pre-study drug screen

Other Exclusions

13. Regular alcohol consumption within 6 months prior to the study defined as:
 - For an average weekly intake of > 14 units for males. One unit is equivalent to 350 mL of beer, 150 mL of wine or 45 mL of 80 proof distilled spirits
14. Smoking or history or regular use of tobacco- or nicotine-containing products within 6 months prior to screening
15. Sensitivity to any of the study treatments, or components thereof, or drug or other allergy that, in the opinion of the investigator or medical monitor, contraindicates participation in the study

6.3. Lifestyle Restrictions

6.3.1. Meals and Dietary Restrictions

- Refrain from consumption of red wine, Seville oranges, grapefruit or grapefruit juice, pomelos, exotic citrus fruits, grapefruit hybrids, or fruit juices from 7 days prior to

the first dose of study medication until completion of all study procedures in each study period after the final dose.

- No water is allowed at least 2 hours before and after dosing. Also, keep resting as much as possible in sitting or semi-sitting position. Water is allowed ad libitum at all other times.
- Once in the clinical unit subjects will not be allowed to eat or drink anything other than provided by the study centre.

6.3.2. Caffeine, Alcohol, and Tobacco

- During each dosing session, participants will abstain from ingesting caffeine- or xanthine-containing products (e.g., coffee, tea, cola drinks, and chocolate) for 24 hours before the start of dosing until collection of the final PK and clinical laboratory sample.
- During each dosing session, participants will abstain from alcohol for 24 hours before the start of dosing until collection of the final PK and clinical laboratory sample.
- Participants will be instructed that use of nicotine-containing products (including nicotine patches) will not be permitted from the screening until collection of the final PK sample.

6.3.3. Activity

- Participants will abstain from strenuous exercise for 48 hours before each blood collection for clinical laboratory tests. Participants may participate in light recreational activities during studies (e.g., watching television, reading).
- Participants will avoid a long direct exposure to sunlight for as long as possible using appropriate sunscreen treatment etc. from the initiation of dosing to follow-up visit when participants will go outside.

6.4. Screen Failures

Screen failures are defined as participants who are screened in the clinical study but are not subsequently randomised. A minimal set of screen failure information is required to ensure transparent reporting of screen failure participants to meet the Consolidated Standards of Reporting Trials (CONSORT) publishing requirements and to respond to queries from regulatory authorities. Minimal information includes demography, screen failure details, eligibility criteria, and any SAEs.

7. TREATMENTS

Study treatment is defined as any investigational treatment(s), marketed product(s), placebo, or medical device(s) intended to be administered to a study participant according to the study protocol.

7.1. Treatments Administered

Study Treatment Name:	GSK1325756H	Placebo
Dosage formulation:	GSK1325756H Tablets, 10 mg are white film coated, round tablets intended for oral administration. GSK1325756H Tablets, 50 mg are white film coated, oval-shaped tablets intended for oral administration,	White oval-shaped tablets which does not include GSK1325756H.
Unit dose strength(s)/Dosage level(s):	10 mg, 50 mg	Not applicable
Route of Administration:	oral	oral
Dosing instructions:	With food and 240 mL (8 oz) water, unless explicitly defined by protocol	With food and 240 mL (8 oz) water, unless explicitly defined by protocol
Manufacturer:	GlaxoSmithKline	GlaxoSmithKline

Note: When 100 mg strength is administrated, subjects receive two doses of 50 mg strength.

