5. STUDY DESIGN

5.1. Overall Design

This study consists of two parts;

Part 1

This is a double blind, placebo-controlled, 3-period crossover, ascending dose, single oral administration in the fed condition (high fat meal). During treatment periods 1 to 3, subjects will be randomized and receive the treatments:

- GSK1325756H 10 mg, single dose, in the fed state
- GSK1325756H 50 mg, single dose, in the fed state
- GSK1325756H 100 mg, single dose, in the fed state, or
- Placebo, single dose, in the fed state

Subjects will have a screening visit within 30 days prior to the first dose of study treatment. A minimum washout period of 7 days from the dose of GSK1325756 will be required between each treatment period. Subjects will receive three treatment periods in the study. Subjects will be housed in the Clinical Research Unit from Day -1 (the day before dosing) through Day 3 for Period 1 and 2, from Day -1 (the day before dosing) through Day 4 for Period 3. Subjects will return to the clinic 7 days (at least) after the previous administration day for Period 1 and 2, and subjects will visit the unit on Day 8 (+/- 1 day) of the last dosing for Part 3 for follow-up.

For each dosing period, the progress to the next period will be determined by GSK medical monitor and investigator based on the blinded safety profiles (AE, clinical laboratory values, vital signs and 12-lead ECG). Furthermore, for the progresses Period 2 to Period 3, GSK medical monitor will determine the appropriateness of the progresses Period 2 to Period 3 based on the result of blood concentration of GSK1325756 assessed by the sponsor's person who is responsible for confirmation of concentration under unblind.

Table 2 Dose regimen for GSK1325756H or placebo

Group	n	Period 1	Washout	Period 2	Washout	Period 3
A	6	10 mg	at least 7 days	50 mg	at least 7 days	Placebo
B	6	10 mg		Placebo		100 mg
C	6	Placebo		50 mg		100 mg

Part 2

This is an open label, 2-way crossover, single oral dose in the fed (low fat meal) and fasted states.

Subjects will have a screening visit within 30 days prior to the first dose of study treatment, two treatment periods separated by at least 7 days, and follow-up. Subjects will be housed in the Clinical Research Unit from Day -1 (the day before dosing) through Day 3 (for Period 1 and 2), and re-visit 7 (± 1) days after the last dose of Period 2 for follow-up.

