7.3. Method of Treatment Assignment

On Day 1 of each Part, participants will be assigned a unique number (randomization number) in ascending numerical order. The randomization number encodes the participant's assignment to one of the 3 sequences in Part 1 and one of the 2 sequences in Part 2, according to the randomization schedule generated prior to the study by the Biomedical Data Sciences Department at GSK. Participants will be randomized in a 1:1:1 ratio to receive sequence (A:B:C) for Part 1, or will be randomized in a 1:1 ratio to receive sequence (D:E) for Part 2. Each participant will be dispensed blinded study treatment, labeled with his unique randomization number, throughout the study.

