7.4. Blinding

Participants for Part 1 will be randomized to one of the treatment sequences, A, B or C. Participants for Part 2 will be randomized to one of the two sequences, D or E.

Investigators, participants and sponsor will remain blinded to each participant's assigned study treatment throughout the course of the study. Although investigational product administering physician will be able to know information on assignment of investigational product, the physician do not inform site staff who are not involved in investigational drug administration about the information of assignment. Also, he/she does not get involved in safety evaluation under blind.

The sponsor's person who is responsible for confirmation of concentration will review blood drug concentration data under unblind.

A participant will be withdrawn if the participant's treatment code is unblinded by the investigator or treating physician. The primary reason for discontinuation (the event or condition which led to the unblinding) will be recorded in the case report form (CRF).

GSK's Global Clinical Safety and Pharmacovigilance (GCSP) staff may unblind the treatment assignment for any participant with an SAE. If the SAE requires that an expedited regulatory report be sent to one or more regulatory agencies, a copy of the report, identifying the participant's treatment assignment, may be sent to investigators in accordance with local regulations and/or GSK policy.

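### Protocol 7.1 sets a round 10 mg tablet against an oval placebo, so in Part 1 Period 1 the listed tablets differ by shape, and no available text hides them from participants

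*Protocol*

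**What the plan says.** Protocol 7.1 describes the products by appearance. For the lowest strength it says "GSK1325756H Tablets, 10 mg are white film coated, round tablets intended for oral administration". The 50 mg tablet is white, film coated and oval. One placebo is listed: "White oval-shaped tablets which does not include GSK1325756H". A note adds "When 100 mg strength is administrated, subjects receive two doses of 50 mg strength". The number of placebo tablets per dose is not given for any period.

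Protocol 5.1 (Table 2) makes Part 1 a double-blind crossover with six participants per sequence:
- A: 10 mg, 50 mg, placebo
- B: 10 mg, placebo, 100 mg
- C: placebo, 50 mg, 100 mg

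On masking, 7.3 says "Each participant will be dispensed blinded study treatment, labeled with his unique randomization number, throughout the study" and 7.4 says "Investigators, participants and sponsor will remain blinded" to the assignment. Section 7.4 accepts that the physician who gives the drug can learn the assignment and sets two limits: "the physician do not inform site staff who are not involved in investigational drug administration about the information of assignment", and "he/she does not get involved in safety evaluation under blind". Section 7.5 asks for nothing special in preparation. Section 7.6 has the nominated physician hand the drug straight to the participant, a second staff member confirm the dose, and staff check the mouth. Sections 7.3 to 7.6 mention no round placebo, double dummy, over-encapsulation, opaque container or covering of the eyes.

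**The concern.** Period 1 contains only two treatments, 10 mg and placebo, and the products listed for them do not look alike. The limits in 7.4 control what staff tell one another. They do not control what the participant sees, and 7.4 names participants among those who must remain blinded.

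Protocol 5.4 gives the purpose of placebo in Part 1: to separate adverse events due to treatment from those that are not. Under 9.1.2 events are found mainly by questioning the participant. Under Appendix 4 the investigator judges causality. SAP 10.9.5 then tabulates drug-related events for Part 1 (Tables 2.3 and 2.4). If participants can work out what they took, their reports are not equally masked across treatments, and the imbalance is greatest at 10 mg.

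**Working it through.** **Inputs.** Tablet shapes and the two-tablet note come from Protocol 7.1. Sequences and group sizes come from 5.1 Table 2 and SAP 10.4.2. The Part 1 total is in Protocol 10.1.1.

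**The plan's own figure.** 6 + 6 + 6 = 18 participants, as stated. Three periods each give 18 × 3 = 54 dosing occasions.

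**Rule.** An occasion counts as identifiable if the shape and number of tablets seen up to that point fit only one treatment for that period. This presumes that the tablets are seen and that the shape key is known or inferred. It also assumes that the oval placebo otherwise looks like the 50 mg tablet.

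**Scenario 1: placebo number matched to the active (1, 1 and 2 tablets).**

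| Sequence | Period 1 | Period 2 | Period 3 |
|---|---|---|---|
| A | round | oval | two ovals |
| B | round | oval | two ovals |
| C | oval | oval | two ovals |

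- Period 1: 12 round (10 mg) against 6 oval (placebo), so 18 of 18 are identifiable.
- Period 2: C is already known (6). A (50 mg) and B (placebo) look the same. 6 of 18.
- Period 3: C is known (6). A (placebo) and B (100 mg) look the same. 6 of 18.
- Total: 18 + 6 + 6 = 30 of 54 (56%).
- By treatment: 10 mg 12/12, placebo 6/18 (33%), 50 mg 6/12, 100 mg 6/12.

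**Scenario 2: one placebo tablet throughout (assumption, since 7.1 gives no number).** Periods 1 and 2 are unchanged. In Period 3, A takes one oval while B and C take two, so A and B separate and all 18 are identifiable.

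- Total in real time: 18 + 6 + 18 = 42 of 54 (78%).
- Placebo: 6 (C, Period 1) + 6 (A, Period 3) = 12/18 (67%).
- Looking back after Period 3, the 12 Period 2 occasions in A and B could also be worked out: 42 + 12 = 54.

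**Scenario 3: tablets concealed, or key neither known nor inferred.** 0 of 54.

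**Source of the Scenario 1 count.** With a round placebo in Period 1 and matched number, all three sequences look round, oval, two ovals, and the count is 0 of 54. All 30 occasions therefore come from the Period 1 shape mismatch.

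**The case against.** The strongest reply is that tablets that can be told apart do not amount to unblinding. Each participant takes only one shape in Period 1, and nothing available tells him which shape is active. Seeing round change to oval in Period 2 does not supply the key and does not separate A from B. This stands, and is why the low figure is 0. It does not settle the matter. Participants are housed in the unit around each dose and could compare tablets, and the protocol offers nothing but lack of comparison to keep them masked.

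Second, 7.4 foresees that the person dosing may recognise the product and keeps that person out of blinded safety evaluation. This also stands and largely protects assessors. Causality judgement would be affected only by a further route, such as a participant describing his tablet, and the documents do not show one.

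Third, concealment may be described elsewhere. The Study Reference Manual and Appendix 7 (country-specific requirements) were not available, and 7.3 does call the treatment blinded. The statement about preparation in 7.5 is weak evidence either way, because that section is about transit, storage and accountability. Absence of a concealment step is therefore established only for the text available.

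A reader might also infer a breach from 7.6, where a second staff member confirms the dose and dosing is by the investigator or a designee. The documents do not support that. Nothing gives the dose checker a role in assessing adverse events, and the designee can be read as the nominated administering physician.

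**Conclusion.** The point holds on the products as listed: followed literally, 7.1 does not deliver the double blind that 5.1 and 7.4 require for participants in Period 1. The tablets differ by shape for all 18, but actual decoding needs the tablet to be seen and the key to be known or inferred.

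The counts of 0, 30 and 42 of 54 are scenarios under stated conditions, not estimates of how often blinding would fail. Two stronger readings are tempting. One is that 30 of 54, with placebo 6/18, is the most that could be identified. It is not, because it depends on matched placebo number, which the protocol does not state. The other is that Part 1 is in effect unblinded or its safety assessors compromised. The documents do not show that, for the reasons given under the objection.

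The consequence is modest. It reaches participant-reported adverse events and their attribution, in a comparison that is descriptive only (Protocol 10.3.1 plans no formal safety comparisons). Pharmacokinetics, laboratory values and ECG intervals are little affected, and Part 2 is open label. The change is still worth making because it is cheap and protects the purpose for which placebo was included.

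**What to change.** Amend Protocol 7.1 and 7.4 in two respects.

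(a) Require Part 1 dosing to be done so that participants and blinded staff do not see the tablets, or list a round placebo matching the 10 mg tablet for Period 1. Concealment costs one extra step in the dosing procedure and needs no new product. If number is matched in later periods, only the 18 Period 1 occasions need it. The round placebo needs a second placebo supply if none exists.

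(b) State that the number of placebo tablets matches the active treatment in each period. This is needed under either option, because a participant who cannot see the tablets may still notice how many he swallows. It adds a line of text and, where placebo would otherwise have been one tablet in Period 3, one more placebo tablet for the six participants in sequence A.

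If a site dosing procedure already conceals the tablets, a reference to it in 7.4 would answer (a).

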7.2. Dose Modification

No dose modification is planned.

7.3. Method of Treatment Assignment

On Day 1 of each Part, participants will be assigned a unique number (randomization number) in ascending numerical order. The randomization number encodes the participant's assignment to one of the 3 sequences in Part 1 and one of the 2 sequences in Part 2, according to the randomization schedule generated prior to the study by the Biomedical Data Sciences Department at GSK. Participants will be randomized in a 1:1:1 ratio to receive sequence (A:B:C) for Part 1, or will be randomized in a 1:1 ratio to receive sequence (D:E) for Part 2. Each participant will be dispensed blinded study treatment, labeled with his unique randomization number, throughout the study.

7.4. Blinding

Participants for Part 1 will be randomized to one of the treatment sequences, A, B or C. Participants for Part 2 will be randomized to one of the two sequences, D or E.

Investigators, participants and sponsor will remain blinded to each participant's assigned study treatment throughout the course of the study. Although investigational product administering physician will be able to know information on assignment of investigational product, the physician do not inform site staff who are not involved in investigational drug administration about the information of assignment. Also, he/she does not get involved in safety evaluation under blind.

The sponsor's person who is responsible for confirmation of concentration will review blood drug concentration data under unblind.

A participant will be withdrawn if the participant's treatment code is unblinded by the investigator or treating physician. The primary reason for discontinuation (the event or condition which led to the unblinding) will be recorded in the case report form (CRF).

GSK's Global Clinical Safety and Pharmacovigilance (GCSP) staff may unblind the treatment assignment for any participant with an SAE. If the SAE requires that an expedited regulatory report be sent to one or more regulatory agencies, a copy of the report, identifying the participant's treatment assignment, may be sent to investigators in accordance with local regulations and/or GSK policy.

7.5. Preparation/Handling/Storage/Accountability

No special preparation of study treatment is required.

1. The investigator or designee must confirm appropriate temperature conditions have been maintained during transit for all study treatment received and any discrepancies are reported and resolved before use of the study treatment.
2. Only participants enrolled in the study may receive study treatment and only authorized site staff may supply or administer study treatment. All study treatments

must be stored in a secure, environmentally controlled, and monitored (manual or automated) area in accordance with the labeled storage conditions with access limited to the investigator and authorized site staff.

3. The investigator, institution, or the head of the medical institution (where applicable) is responsible for study treatment accountability, reconciliation, and record maintenance (i.e., receipt, reconciliation, and final disposition records).
4. Further guidance and information for the final disposition of unused study treatment are provided in the Study Reference Manual (SRM).
 - Under normal conditions of handling and administration, study treatment is not expected to pose significant safety risks to site staff.
 - A Material Safety Data Sheet (MSDS)/equivalent document describing occupational hazards and recommended handling precautions either will be provided to the investigator, where this is required by local laws, or is available upon request from GSK.

